6.3.2.5 Simpson-Angus Scale

The SAS is a measure of extrapyramidal side effects (Simpson, 1970). Ten items including rating gait, arm dropping, shoulder shaking, elbow rigidity, wrist rigidity, leg pendulousness, head rotation, glabella tap, tremor, and salivation are rated on a scale from 0 (normal) to 4 (extreme in severity). The SAS should be conducted by the investigator or an expert site-based rater in a room where the patient can walk a sufficient distance to allow a natural pace (e.g., 15 paces). Each side of the body should be examined. The SAS is to be completed at baseline and periodically throughout the study as specified in the schedule of events (Table 6–1 and Table 6-2 for Parts A and B, respectively).

6.3.2.6 Vital Sign Measurements

Vital signs will be measured at screening and at every subsequent scheduled clinic visit (Table 6–1 and Table 6-2 for Parts A and B, respectively). Details of the vital sign measurements are presented in Section 6.1.5.

6.3.2.7 ECG Assessments

The ECG assessments will be performed at screening and periodically throughout the study, as scheduled (Table 6–1 and Table 6-2 for Parts A and B, respectively). Details of the ECG assessments are presented in Section 6.1.4.

6.3.2.8 Physical and Neurological Examination

The physical and neurological examinations will be conducted at screening and periodically throughout the study, as scheduled (Table 6–1 and Table 6-2 for Parts A and B, respectively). Details of the physical and neurological examinations are presented in Section 6.1.3.

6.4 Safety Monitoring Committee

No safety monitoring committee will be used for the study.

6.5 Laboratory Analyses

Blood and urine samples collected from patients will be forwarded to a central laboratory for analysis. Further details regarding sample collections, processing and specific testing can be found in the study reference manual.

All samples for clinical laboratory analysis will be collected after an overnight fast (≥ 10 hours), for all visits subsequent to screening, prior to dosing with study drug. Samples for clinical laboratory analysis will be used only for the evaluation of safety and tolerability.

Any abnormal laboratory test results (hematology, clinical chemistry, or urinalysis) or other safety assessments (e.g., ECGs, vital sign measurements), including those that worsen from baseline, felt to be clinically significant, in the medical and scientific judgment of the investigator, are to be recorded as AEs or SAEs.

However, any clinically significant safety assessments that are associated with the underlying disease, unless judged by the investigator to be more severe than expected for the patient's condition, are not to be reported as AEs or SAEs.

The following clinical analytes will be determined:

Hematology: hematocrit; hemoglobin; HbA_{1c}; red blood cell count with indices (mean corpuscular volume, mean corpuscular hemoglobin, and mean corpuscular hemoglobin concentration); reticulocytes; white blood cell count and differential (neutrophils, lymphocytes, monocytes, eosinophils, and basophils) reported as percent (%) and absolute values; and platelets (platelet count, prothrombin time and partial thromboplastin time, international normalization ratio).

Clinical chemistry: albumin; alkaline phosphatase; blood urea nitrogen; gamma-glutamyl transferase; calcium; creatinine; glucose; insulin; cholesterol (high-density lipoprotein and low-density lipoprotein [LDL] [calculated] and homogenous LDL will be reported, and homogenous LDL will be reflexed if a patient's triglycerides are >400); triglycerides; phosphate; potassium; prolactin, ALT; AST; lactate dehydrogenase; sodium; chloride; bilirubin (total, direct); total protein; uric acid; creatine phosphokinase; and thyroid panel (at screening only, thyroid-stimulating hormone will be assayed and if the result is abnormal, the free thyroxine and free triiodothyronine will be assayed).

Urinalysis: macroscopic (pH, specific gravity, glucose, protein, ketones, nitrates, blood) and microscopic – report only if present (red blood cells/high-power field, white blood cells/high-power field, casts, epithelial cells, crystals, granulation).

Serology: anti-HIV antibodies, hepatitis B surface antigen, and hepatitis C antibody (only during screening).

[REDACTED]

[REDACTED]

[REDACTED]

[REDACTED]

[REDACTED]

[REDACTED]

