6.3 Safety and Tolerability Assessments

All patients who receive study drug will be evaluated for safety. Safety assessments will include incidence of AEs, suicidality assessment by the C-SSRS, mania assessment by the YMRS, movement disorder assessment by the AIMS, BARS and SAS, clinical laboratory evaluations, ECG evaluations, vital sign measurements, and physical examination and neurological findings.

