6.3.1 Adverse Events

The investigator is responsible for reporting all AEs that are observed or reported during the study, regardless of their relationship to study drug or their clinical significance.

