6.3.1.1 Definition of Adverse Event

An AE is any untoward medical occurrence in a study patient administered a study drug, whether or not considered drug related. This can be any unfavorable and unintended sign (such as an abnormal laboratory finding), symptom, or disease temporally associated with the use of a study drug, without any judgment of causality.

The AE may be:

- A new illness;
- A worsening sign or symptom of the condition under treatment, or of a concomitant illness;
- An effect of the study medication, including comparator; or
- A combination of 2 or more of these factors.

No causal relationship with the study medication or with the clinical study itself is implied by the use of the term AE.

Surgical procedures themselves are not AEs; they are therapeutic measures for conditions that require surgery. The condition for which the surgery is required may be an AE. Planned surgical measures, if permitted by the clinical study protocol and the conditions leading to those measures are not AEs.

All AEs fall into the categories of “nonserious” or “serious (Sections 6.3.1.2 and 6.3.1.3).

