7.1.5 Safety Endpoints (Parts A and B)

- AEs;
- YMRS total score;
- MADRS score (safety endpoint for Part B only);
- C-SSRS scores;
- AIMS scores;
- BARS scores;
- SAS score;
- Physical examination and neurological findings;
- Vital signs (blood pressure, heart rate), weight, and height (height, only at screening);
- ECGs;
- Clinical laboratory evaluations.

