7.5.1 Patient Disposition, Analysis of Demographics and Other Baseline Characteristics

Patient disposition will be summarized for each Part by treatment group, when applicable, and overall, including incidence of screen failure, and treatment or study discontinuation and the corresponding reasons. The number and percentage of randomized patients who discontinued due to an adverse event associated with worsening of bipolar depression will be

summarized. Similarly, the number and percentage of randomized patients who discontinued due to an adverse event not associated with worsening of bipolar depression will also be presented. Time to treatment discontinuation due to all reasons, adverse events, lack of efficacy, or due to any other reason of special interest will be evaluated separately using the Kaplan-Meier method, where patients who complete the On-Treatment Period or who discontinue for a reason other than the one being evaluated will be censored. The Log-rank test will be used to compare the time to discontinuation between each treatment group and the placebo group (Part A).

Demographic and baseline characteristics, including bipolar disorder diagnosis and bipolar disorder baseline efficacy measures, will be summarized for each part by treatment group for Part A only using descriptive statistics. No inferential statistics will be presented.

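### Protocol 6.5 exempts some disease-related safety findings from AE and SAE reporting, conflicts with 6.3.1 as written, and is not expressly limited to laboratory, ECG and vital-sign findings

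*Protocol*

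**What the plan says.** Protocol 6.5 (Laboratory Analyses) has two consecutive statements on reporting. The first covers abnormal laboratory results and "other safety assessments (e.g., ECGs, vital sign measurements), including those that worsen from baseline". If the investigator considers them clinically significant, they are recorded as AEs or SAEs. The second takes part of this back for "any clinically significant safety assessments that are associated with the underlying disease". Its instruction is that these, "unless judged by the investigator to be more severe than expected for the patient's condition, are not to be reported as AEs or SAEs", so the default for them is non-reporting.

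The AE rules are in 6.3.1 and its subsections:

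- 6.3.1 makes the investigator responsible for "reporting all AEs that are observed or reported during the study, regardless of their relationship to study drug or their clinical significance".
- 6.3.1.1 counts as an AE "A worsening sign or symptom of the condition under treatment, or of a concomitant illness".
- 6.3.1.2 defines an SAE mainly by outcome, including hospitalization.
- 6.3.1.8 requires notification within 24 hours of every SAE, related to study drug or not.

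The protocol says what it means by safety assessments in 6.3: "Safety assessments will include incidence of AEs, suicidality assessment by the C-SSRS, mania assessment by the YMRS", followed by the movement scales, laboratory tests, ECGs, vital signs and examinations. Section 6.3.2, headed Safety Assessments, names the C-SSRS and YMRS again.

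**The concern.** In this trial the underlying disease is bipolar disorder. The safety assessments most naturally associated with it are the mania and suicidality scales. A site that applies 6.5 as written could leave a clinically significant YMRS or C-SSRS finding off the AE page because it seems usual for the illness. Under 6.3.1 and 6.3.1.1 the same finding has to be recorded.

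Incidence of AEs is a safety objective of Part A and the first item of the Part B primary objective. An event that a site never records may not be recoverable at analysis. The test for omission is what the investigator expects for that patient's condition. The protocol does not define this, and about 60 sites would apply it.

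**Working it through.** No figure in the plan depends on this point, so the check is a comparison of texts, followed by a note on size.

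**1. Is there a conflict?** Take a patient whose YMRS rises after baseline. The investigator thinks the rise clinically significant, attributes it to bipolar disorder, and judges it no worse than expected.

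| Section | What it tells the site |
|---|---|
| 6.5, first statement | Record as an AE or SAE |
| 6.5, second statement | Do not report |
| 6.3.1 | Report, whatever the relationship or clinical significance |
| 6.3.1.1 | Worsening of the treated condition is an AE |
| 6.3.1.2 and 6.3.1.8 | If a seriousness criterion is met, notify within 24 hours |

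The site cannot follow every row. Section 6.3.1.9, headed Exceptions, does not help: it deals only with urgent-care and emergency-room visits.

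**2. Does the wording reach the C-SSRS and YMRS?** The first statement in 6.5 goes beyond laboratory tests, and ECGs and vital signs are given only as examples. The second applies to any clinically significant safety assessment and adds no limit. Sections 6.3 and 6.3.2 place both scales under that term. The wording therefore permits this reading but does not compel it.

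**3. Does the exception for findings worse than expected remove the conflict?** No. It narrows the exemption, but 6.3.1, 6.3.1.1, 6.3.1.2 and 6.3.1.8 contain no such threshold. Findings at or below what the investigator expects are still treated differently by the two sets of rules.

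**4. Which analyses depend on AE records?** SAP 16.1 builds TEAEs only from recorded AEs. SAP 16.1.1 identifies AEs leading to discontinuation from the AE page, and SAP 16.1.2 takes SAEs from the same page. Protocol 7.5.1 and SAP 9 count randomized patients who "discontinued due to an adverse event associated with worsening of bipolar depression", so the planned analysis presupposes that disease worsening is recorded as an AE.

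**5. What is captured elsewhere?** SAP 16.6.5 tabulates emergent and worsening suicidal ideation, serious ideation, behavior and attempts directly from the C-SSRS. SAP 16.6.4 summarizes observed YMRS and change by treatment and visit. It gives no category for emergent mania, so in the text that can be read, the incidence of mania rests on AE reporting.

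**6. Size.** Suppose the true incidences are p1 on drug and p0 on placebo, and the same fraction f of events goes unrecorded in both arms. Then:

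- recorded difference = (1 − f)p1 − (1 − f)p0 = (1 − f)(p1 − p0), which is smaller than the true difference;
- recorded ratio = (1 − f)p1 / (1 − f)p0 = p1/p0, unchanged but based on fewer events.

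Part B has no comparison arm, so the recorded incidence (1 − f)p is itself the result. The documents give neither f nor the incidences, so no number follows.

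**The case against.** The strongest reply is that the sentence is about laboratory-type findings. It stands under Laboratory Analyses, opens by qualifying a statement whose only examples are ECGs and vital signs, and is followed by the analyte list. The list in 6.3 also includes AE incidence, which cannot sensibly be inserted into 6.5 as a finding. The governing AE rules are in 6.3.1 and have no such exemption, and 6.3.1.7 requires recording of whatever patients volunteer or report when questioned. This makes the narrow reading plausible. It does not supply the missing limit, and sites need a single reading.

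The reply stands against four stronger inferences that a reader might draw:

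- *AEs of worsening bipolar depression cannot be counted.* Findings worse than expected remain reportable, and SAP 9, Table B, keeps a dedicated discontinuation reason. The list in 6.3 does not name the MADRS, and 7.1.5 has "MADRS score (safety endpoint for Part B only", whereas the count concerns randomized patients, that is, Part A.
- *Suicide attempts or hospitalizations for mania escape 24-hour notification.* Section 6.5 mentions SAEs, so confusion is possible. But it speaks of assessments, and an event meeting 6.3.1.2 still falls under 6.3.1.8.
- *The suicidality and mania signals are lost to the trial.* They are not: SAP 16.6.4 and 16.6.5 summarize both scales without using AE records.
- *The comparison between arms is biased in one direction.* Part A is double-blind, and nothing in the documents suggests that these judgments would differ by arm.

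**Conclusion.** The conflict is real and textual. As written, 6.5 allows a site to omit disease-related findings that 6.3.1 and 6.3.1.1 require it to record, and the YMRS and C-SSRS fall within its terms. The supported conclusion is that emergent mania, suicidality and similar events may be under-recorded, inconsistently across sites, in the AE, TEAE and SAE data. The documents do not show that this happened or how large it would be.

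The conclusion assumes that at least some sites take 6.5 at its word, and that site instructions not seen here, such as the study reference manual, do not already narrow it. The primary efficacy analysis is not affected.

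**What to change.** Reconcile 6.5 with 6.3.1, 6.3.1.1, 6.3.1.2 and 6.3.1.8:

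- Limit the 6.5 exemption expressly to laboratory, ECG and vital-sign findings.
- State that 6.5 does not override the AE and SAE definitions.
- State that any worsening of the condition under treatment is recorded as an AE under 6.3.1.1, and as an SAE when a 6.3.1.2 criterion is met.
- Attach no further test of what is expected or clinically significant to that last rule. Section 6.3.1 requires reporting regardless of clinical significance, so such a test would bring the conflict back.

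The cost is a short amendment to one paragraph, a memo to sites, and somewhat more AE records. The change concerns reporting only and does not alter treatment.

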6.7 Sample Collections

6.7.3 Frequency and Volume of Blood Collection

Blood samples will be collected for laboratory assessments, hepatitis and HIV screening, determination of plasma concentrations of ITI-007 and metabolites, and also for the assessment of protein and genetic biomarkers. The sampling times for all blood sample

collections are given in Table 6–1 and Table 6–2 for Parts A and B, respectively (Schedules of Events).

The estimates of blood sample volume and sample numbers are presented in Table 6–5.

Table 6–5 Number and Volume of Blood Samples for Part A

| Study Day/Visit | PK | Number of Blood Samples | | | | |
|--|-----------|-------------------------|-------------------|-----------------------|---------------------|---------------|
| | | Protein Biomarker | Genetic Biomarker | Laboratory Assessment | Hepatitis Screening | HIV Screening |
| Screening | | | | | X | X |
| Day 1 | | X | X | | X | |
| Day 8 | X | X | | | X | |
| Day 22 | X | X | | | X | |
| Day 43 | X | X | | | X | |
| Day 57 | | | | | X | |
| Total number of samples | 4 samples | 4 samples | 1 sample | 6 samples | 1 sample | 1 sample |
| Total maximum volume ¹ | 40 mL | 40 mL | 10 mL | 60 mL | 10 mL | 10 mL |
| Total blood volume per patient: up to 170 mL | | | | | | |

¹ Each sample will have a volume of up to 10 mL.

Note: Additional blood samples may be collected for repeat safety follow up.

Table 6–6 Number and Volume of Blood Samples for Part B

| Study Day | Laboratory Assessment | Hepatitis Screening | HIV Screening |
|-----------------------------------|-----------------------|---------------------|---------------|
| Screening | X | X | X |
| Days 25, 75, 125, 175, 189 | X | | |
| Days 75, 175, 189 | | | |
| Total number of samples | 6 samples | 1 sample | 1 sample |
| Total maximum volume ¹ | 60 mL | 10 mL | 10 mL |

¹ Each sample will have a volume of up to 10 mL.

Note: Additional blood samples may be collected for repeat safety follow up.

6.8 Pregnancy

Pregnancy is not regarded as an AE unless there is a suspicion that an investigational product may have interfered with the effectiveness of a contraceptive medication. Any pregnancy that occurs during study participation must be reported using a clinical study pregnancy form. The patient must stop study drug immediately after pregnancy is discovered and have an Early Termination visit as soon as possible. Additionally, each pregnancy must be reported to ITI within 2 weeks of learning of its occurrence. The pregnancy must be followed up to determine outcome (including spontaneous miscarriage, elective termination, normal birth, or congenital abnormality) and status of mother and child, even if the patient was discontinued from the study. Pregnancy complications and elective terminations for medical reasons should not be reported as an AE or SAE. Spontaneous miscarriages must be reported as an SAE.

Any SAE occurring in association with a pregnancy, brought to the investigator's attention after the patient has completed the study, and considered by the investigator as possibly related to the study treatment, must be promptly reported to ITI.

7 Statistical and Analytical Plan

A formal and detailed statistical analysis plan (SAP) for Part A will be finalized prior to the planned IA, and will provide further details regarding the definition of analysis endpoints, analysis methodology, and the IA to address all study objectives. Similarly, a SAP for Part B will be finalized prior to database lock. Changes made to the data analysis methods as described in the protocol will be documented in the SAP and will not necessitate a protocol amendment. All departures from the statistical analyses described in the approved protocol, whether made before or after database lock, will be documented, and justified in the final clinical study report.

Blinded (Part A) and unblinded (Part B) data review will be conducted prior to unblinding the patients' treatment assignments (Part A) or finalizing the outputs (Part B) for assessing the accuracy and completeness of the study database and defining analysis datasets. An unblinded review of Part A interim data will be conducted by an independent external unblinded Data Monitoring Committee (DMC) in accordance with the IA plan.

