6.3.1.2 Definition of Serious Adverse Event

An SAE is defined as any untoward medical occurrence that at any dose:

- Results in death;
- Is life threatening;
- Requires hospitalization or prolongation in existing hospitalization;
- Results in persistent or significant disability or incapacity; or
- Is a congenital anomaly or birth defect.

The term “life threatening” refers to an event in which the patient is at risk of death at the time of the event; it does not refer to an event, which hypothetically might have caused death if it were more severe.

Medical and scientific judgment should be exercised in deciding whether an AE is serious. Some important medical events that may not result in death, be life threatening, or require hospitalization may be considered SAEs when they may jeopardize the patient such that medical or surgical intervention is needed to prevent 1 of the outcomes previously listed. Examples of such medical events include intensive emergency treatment for an allergic reaction, blood dyscrasias or convulsions that do not result in inpatient hospitalization, and the development of drug dependency or drug abuse.

If either the sponsor or principal investigator believes that any event is serious, the event must be considered and evaluated by the sponsor for possible expedited reporting.

Clarification of the difference between "serious" and "severe":

The term “severe” is often used to describe the intensity (severity) of a specific event (as in mild, moderate, or severe myocardial infarction); the event itself, however, may be of relatively minor medical significance (such as a severe headache). This is not the same as “serious,” which is based on patient/event outcome or action criteria usually associated with events that pose a threat to a patient’s life or functioning. Seriousness (not severity) serves as a guide for defining regulatory reporting obligations.

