6.3.1.8 Notification About Serious or Unexpected Adverse Events

The investigator will review each SAE (Section 6.3.1.2) and evaluate the intensity and the causal relationship of the event to study drug. All SAEs will be recorded from signing of informed consent until follow-up.

The investigator is responsible for providing notification to the sponsor or designee of any SAE, whether deemed related to study drug or not, that a patient experiences during their participation in study within 24 hours of becoming aware of the event.

As a minimum requirement, the initial notification should provide the following information:

- Study number
- Patient number
- Gender
- Date of birth
- Name of investigator and full study site address
- Details of SAE
- Criterion for classification as “serious”
- Study drug code, or name if unblinded, and treatment start date and stop date, if applicable
- Date of SAE onset
- Causality assessment (if sufficient information is available to make this classification)

The sponsor will request clarification of omitted or discrepant information from the initial notification. The investigator or an authorized delegate is responsible for faxing the requested information to the sponsor within 24 hours of the sponsor's request.

Initial reports of SAEs must be followed later with detailed descriptions, including clear photocopies of other documents as necessary (e.g., hospital reports, consultant reports, autopsy reports), with the study patient's personal identifiers removed. All relevant information obtained by the investigator through review of these documents will be recorded and faxed to the sponsor within 24 hours of receipt of the information. If a new SAE Report Form is faxed, then the investigator must sign and date the form. The sponsor may also request additional information on the SAE, which the investigator or an authorized delegate must fax to the sponsor within 24 hours of the request.

The SAE reporting contact information will be provided to all participating study sites by the contract research organization (CRO) before study initiation.

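### Protocol 6.8 tells sites to report pregnancy complications as neither AE nor SAE, which contradicts the protocol's own SAE definition and 24-hour rule when the complication is serious

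*Protocol*

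**What the plan says.** Protocol 6.8 handles pregnancy outside the usual AE route. Each pregnancy goes on a dedicated form, reaches the sponsor within 2 weeks of being learned of, and is followed to its outcome, including how mother and child fare. The section then instructs: "Pregnancy complications and elective terminations for medical reasons should not be reported as an AE or SAE". The next sentence goes the other way for one outcome: "Spontaneous miscarriages must be reported as an SAE". A final paragraph requires prompt reporting of a pregnancy-associated SAE that comes to light after the patient has completed the study, if it is judged possibly related.

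The general safety rules are broader:

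- Section 6.3.1: "The investigator is responsible for reporting all AEs that are observed or reported during the study, regardless of their relationship to study drug".
- Section 6.3.1.1 does not count a surgical procedure as an AE, but adds: "The condition for which the surgery is required may be an AE".
- Section 6.3.1.2: "An SAE is defined as any untoward medical occurrence that at any dose" meets one of five criteria. These include a threat to life and "Requires hospitalization or prolongation in existing hospitalization".
- Section 6.3.1.8 makes the investigator notify "any SAE, whether deemed related to study drug or not, that a patient experiences during their participation in study within 24 hours"; the clock starts at awareness.
- Section 6.3.1.9, the list of exceptions, deals only with urgent care and emergency room visits.
- Sections 6.3.1.6 and 6.3.1.7 collect AEs from consent to the end of participation, and SAEs up to 30 days after the last dose.

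SAP 16.1.2 builds the SAE summary from events marked serious on the Adverse Events page of the eCRF. SAP section 2 limits that plan to Part A.

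**The concern.** For one class of event a site holds two instructions that cannot both be obeyed. If an enrolled patient is admitted with a pregnancy complication, 6.3.1.2 makes the event an SAE and 6.3.1.8 starts a 24-hour clock. Section 6.8 says not to report it at all as an AE or SAE. Because 6.8 is the section specific to pregnancy, a coordinator dealing with a pregnant patient would probably follow it.

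Two things are then lost. The first is rapid notification, which depends on the event being called an SAE. The second is the analysis record: an event never entered on the AE page cannot appear in a summary drawn from that page. Nothing in the efficacy analysis is touched.

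**Working it through.** The plan states no figure to reproduce. The check sets the rules side by side.

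**Step 1. Classify each kind of event that occurs during participation, except where noted.**

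| Event | General rules (6.3.1 to 6.3.1.8) | Section 6.8 | Conflict? |
|---|---|---|---|
| Maternal complication that is life threatening or leads to hospitalization | SAE, 24-hour notice, AE page | Neither AE nor SAE | Yes |
| Maternal complication meeting no seriousness criterion | AE, AE page | Not an AE | Yes, AE recording only |
| Termination as a procedure | Not itself an AE, by analogy with the surgery rule in 6.3.1.1 | Neither AE nor SAE | No |
| Patient's medical condition that led to the termination | May be an AE; an SAE if it meets a criterion | Not separated from the termination, so a site would read it as exempt | Yes |
| Spontaneous miscarriage | SAE if it meets a criterion | Always an SAE | No loss of reporting |
| Congenital anomaly | A listed criterion: "Is a congenital anomaly or birth defect" | Not named in the exemption; listed as an outcome to follow | No direct conflict |
| Possibly related SAE learned of after study completion | Sponsor to be contacted (6.3.1.6) | Promptly reported | No |

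**Step 2. Look for text that resolves the conflict.** Section 6.3.1.2 has no pregnancy exemption. The exceptions in 6.3.1.9 do not mention pregnancy, and they restore SAE reporting once a patient is admitted. The last paragraph of 6.8 accepts that SAEs can arise with a pregnancy, but reaches only those learned of after study completion and judged possibly related. It does not cover events during participation, where 6.3.1.8 applies regardless of causality.

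**Step 3. Follow the clocks.** The 24 hours in 6.3.1.8 run from awareness of an SAE. The 2 weeks in 6.8 run from learning of the pregnancy. Once the event is not called an SAE, the first clock never starts. The second concerns the pregnancy, not a complication that appears later. Outcome follow-up in 6.8 carries no deadline. The complication therefore has none.

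**Step 4. Follow the data.** Under 6.3.1.7, AEs are recorded on the AE page of the eCRF, and SAP 16.1.2 takes SAEs from that page. An event withheld under 6.8 is therefore absent from the Part A SAE summary. Protocol 7.5.8 plans SAE summaries for Part B too, but the Part B SAP is not among the documents, so its data source cannot be checked.

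**Step 5. Gauge the count.** The documents give no pregnancy rate. Inclusion criterion 5 of Part A defines acceptable contraception by a failure rate below 1% per year with correct use. As an illustration, assume that all 549 patients could become pregnant, use contraception correctly, and complete treatment:

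- Part A: 549 × 42/365 × 0.01 = 0.63 pregnancies.
- Parts A and B: 549 × (42 + 175)/365 × 0.01 = 3.3 pregnancies.

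Men, women of non-childbearing potential and early leavers lower these figures; imperfect contraceptive use raises them. Serious complications would be a subset. The figures show only that the number is likely to be small.

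**The case against.** The best defence is that 6.8 diverts these events and does not discard them. The sponsor receives the pregnancy form, and sites must follow each pregnancy to its outcome and record the status of mother and child, even after the patient has left the study. Miscarriage remains an SAE. Under 6.3.1.2, any event that the sponsor or principal investigator believes to be serious must be evaluated for possible expedited reporting, and 6.3.1.9 allows doubtful cases to be discussed with the medical monitor. Study drug stops when pregnancy is found, so many outcomes would fall after the 30-day window under either rule. All of this stands, and it limits the consequences. It does not remove the contradiction, because none of these routes puts a serious complication during participation on the 24-hour clock or on the AE page.

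Some stronger readings are tempting but are not supported:

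- A reader might compare 2 weeks with 24 hours and infer a 14-fold delay (336/24). The two clocks have different triggers, so the ratio measures nothing.
- A reader might infer that every medically indicated termination, or every fetal anomaly, is an SAE that 6.8 suppresses. Section 6.3.1.1 separates a procedure from the condition behind it, and anomalies are not named in the exemption.
- A reader might infer that serious outcomes are hidden from the sponsor or barred from expedited review. The follow-up duty in 6.8 and the judgement clause in 6.3.1.2 say otherwise.
- A reader might rank miscarriage as milder than the exempted events and call 6.8 perverse. The documents contain no such ranking.

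**Conclusion.** The contradiction is real but narrow. For a pregnancy complication during participation that is life threatening or requires hospitalization, or for a patient's serious medical condition that leads to a termination, 6.8 cannot be followed together with 6.3.1.2 and 6.3.1.8. For complications that are not serious, the conflict is with ordinary AE recording under 6.3.1.

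The consequence is loss of 24-hour notification and absence from the Part A SAE summary. It is not loss of all knowledge of the event. The conclusion assumes that sites follow 6.8 as written, and that its exemption is read as covering the condition behind a termination as well as the termination itself.

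The number of affected events cannot be derived from the documents and is likely to be small. The point is still worth fixing because it concerns a safety-reporting rule, each affected event could be serious, and the remedy is cheap.

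**What to change.** Amend the sentence in 6.8 so that it agrees with 6.3.1.2 and 6.3.1.8. One wording that would do so:

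*Pregnancy itself, and an elective termination as a procedure, are recorded on the pregnancy form. A pregnancy complication, or the medical condition leading to a termination, is recorded as an AE. It is reported as an SAE under Section 6.3.1.8 when it meets a criterion in Section 6.3.1.2. The observation period and the 30-day post-dose window in Section 6.3.1.6 apply.*

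The miscarriage sentence can stay. The last paragraph of 6.8 can continue to govern events that come to light later. An open-ended duty to report during or after the study should be avoided, since it would override 6.3.1.6 to 6.3.1.8 and the possibly-related condition in 6.8, and so create a new inconsistency.

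The cost is one sentence in a protocol amendment with IRB submission, a reminder to sites, and probably very few extra AE or SAE forms. SAP 16.1.2 needs no change, because events entered on the AE page would flow into its summary.
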